The study is a randomized trial with a control group and an intervention group. Patients will be randomized via Research Electronic Data Capture (Redcap), a secure web application for building and managing databases and online questionnaires. The system was developed at Vanderbilt University, which released the first version in 2008 (22). Patients will be randomized to the control or intervention group. Randomization will be stratified by gender. Patients in the intervention group will receive systematic and structured nursing guidance regarding their adherence, which includes proper use of nasal irrigation once or twice daily, nasal steroid/drops, use of inhaled medications, follow-up of smoking status. The intervention group will receive guidance videos which have been prepared prior to the study and will be standard for the intervention group. Guidance videos will cover the correct use of nasal irrigation, inhalation steroid, and nasal steroid/drops. The control group and intervention group will receive twice a week text message reminders to take their medications and to rinse their nose.

Their adherence will be measured via MARS-5-N and MARS-5-L f. Total MARS-5-N/L will be measured at their initial visit and four months after teaching or usual care. The same form will be given at both visits. Patients in the control group will not receive systematic and structured nursing care regarding their adherence, but their adherence will be measured via MARS-5-N and MARS-5-L max score is 50 when measuring a adherence in global airways. In a pilot study, mean (SD) 20.4 (6.28) is found for MARS-5-L, and for MARS-5-N mean 20.7 (5.57) is found. 41 points correspond to 80% of total of both MARS-5-L and MARS-5-N. A satisfactory adherence should be 80%. In another pilot study, patients were measured twice with at least one month in between. Here, the mean of the inter-individual difference at MARS-5-L/N first and second time is equal to 5.34(2.62). These two pilot studies will be used for the final power calculation.

Statistics data analysis and power calculation

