The statistical analysis of data is performed using IBM SPSS Statistics. Results will be presented as mean, SD, range and 95% CI. The parametric data will be compared using paired and unpaired tests, and non-parametric data using Wilcoxon Signed-Ranks Test and Mann-Whitney Test, respectively. Categorical variables are tested by chi-square test. A P-value <0.025 is considered significant for a pooled MARS-5-N and MARS-5-L For a pooled MARS5-L/N questionnaire, the total score would be 25x2= a total of 50 points theoretically. A safe difference is calculated from the intraindividual difference detected in the pilot study (mean 5.34 (2.62)), but based on the pilot study an SD and mean are calculated on the difference between MARS-5-L/N, which corresponds to an SD 5.34 and mean 2.62. With a MIREDIF of 5 and the largest SD of 6.28 by single measurement with a p-value of 0.025% (0.05/2) because there are two schedules and a power 80%, this would require 36 patients in each group including a dropout of 20%.

In addition, ensuring that MARS-5-N/L are both above 80% (the standard requirements for good adherence); and hoping for 100% adherence in the intervention group, versus 80% in the control group, this would require 39 in each group. - And including the 20% dropout rate, the total population would be 47 in each group.

Project participants

[name], nurse, Department of Otolaryngology and Audiology

[name], clinical nurse specialist and ph. Student, Department of Ear, Nose and Throat Surgery and Audiology

[name], Senior Physician, Department of Ear, Nose and Throat Surgery and Audiology

[name], Professor, MD, Department of Ear, Nose and Throat Surgery and Audiology

Risks and side effects

There are no serious side effects associated with participation in the trial. There may be a risk that patients in the control group of the study may have a worse prognosis/prognosis than patients achieving good adherence (80%) in the intervention group. To reduce this risk, patients in the control group are offered the same guidance as those in the intervention group at the end of the trial.

Information from patient records

No personal data will be collected from patient records. Data included in the study are from patient questionnaires and from results of clinical objective tests.

Processing of personal data

The project is carried out in compliance with the Data Protection Regulation and the Data Protection Act.

Economy

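### The pilot retest mean and SD are swapped within one sentence, and the target is 5 points in the power calculation but 4 in the primary outcome, so the target's basis cannot be checked and the stated 80% power does not apply to the primary outcome as worded

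*Combined protocol and SAP*

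**What the plan says.** Material and method reports two pilots. One measured each scale once: "mean (SD) 20.4 (6.28) is found for MARS-5-L, and for MARS-5-N mean 20.7 (5.57) is found". In the other, patients completed the questionnaire twice, at least a month apart, and "the mean of the inter-individual difference at MARS-5-L/N first and second time is equal to 5.34(2.62" in brackets. The section adds: "These two pilot studies will be used for the final power calculation".

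The section on statistics and power returns to the second pilot: "A safe difference is calculated from the intraindividual difference detected in the pilot study (mean 5.34 (2.62" in brackets. The same sentence continues that an SD and mean were calculated on the difference between MARS-5-L/N, "which corresponds to an SD 5.34 and mean 2.62". No value or formula for the safe difference follows. The next sentence begins "With a MIREDIF of 5 and the largest SD of 6.28 by single measurement", adds "a p-value of 0.025% (0.05/2) because there are two schedules" and 80% power, and arrives at 36 per group including 20% dropout. A second calculation, for 100% against 80% adherence, gives 39 per group, or 47 with dropout.

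The target appears twice before that, in nearly the same wording: an improvement of 5 points under Hypothesis and research questions, and of 4 points in the primary outcome under Outcomes.

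**The concern.** There are two linked faults in the basis of the sample size.

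First, the same two figures are assigned to mean and SD in opposite ways. The plan names this pilot as the source of its safe difference and as an input to the power calculation, so a reader needs to know which figure is which. The label also moves from an inter-individual to an intra-individual difference, so even the quantity measured is unclear.

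Second, the target takes two values. The 80% power is calculated for 5 points, while the primary outcome names 4. Power falls quickly as the target difference shrinks, so the two values imply materially different trials. A readable derivation from the pilot could have shown which value was intended, but the plan does not give one.

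**Working it through.** **Inputs**
- Difference: 5 (power calculation, research question) or 4 (primary outcome).
- SD: 6.28, the single-measurement MARS-5-L value that the plan uses.
- Alpha: 0.025. It is printed with a percent sign, but 0.05/2 is given beside it. Two-sided is assumed.
- Power 80%, dropout 20%.

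**Formulas (normal approximation)**
- n per group = 2 × (SD/difference)² × (z₁ + z₂)², with z₁ = 2.2414 for two-sided 0.025 and z₂ = 0.8416 for 80% power. The squared sum is 9.505.
- Power = Φ(difference / [SD × √(2/n)] − 2.2414).

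**Step 1: the plan's own figure**
- 2 × (6.28/5)² × 9.505 = 29.99, so 30.
- 30 × 1.2 = 36, which matches the stated 36 per group.
- Alpha read literally as 0.025% would give 65 before dropout, so 0.025 is the reading that fits.
- Neither 5.34 nor 2.62 enters.

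**Step 2: the same method with the primary outcome's 4 points**
- 2 × (6.28/4)² × 9.505 = 46.9, so 47 per group before dropout.

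**Step 3: power for 4 points at the sizes in the plan**

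| Completers per group | Source | SD × √(2/n) | 4 / that − 2.2414 | Power |
|---|---|---|---|---|
| 30 | 36 less the dropout allowance | 1.621 | 0.226 | about 59% |
| 39 | 47 less the dropout allowance | 1.422 | 0.571 | about 72% |

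The plan's 47 per group happens to equal the 47 from step 2, but the plan's figure already includes dropout (39 × 1.2 = 46.8). It would give 80% power for 4 points only if nobody dropped out.

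**Step 4: what the pilot labels imply**

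| Labelling | Where | Mean against 5 and 4 | 1.96 × SD |
|---|---|---|---|
| Mean 5.34, SD 2.62 | Material and method; first half of the statistics sentence | both targets below the mean | 5.14 |
| Mean 2.62, SD 5.34 | second half of the same sentence | both targets above the mean | 10.47 |

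Under the first labelling, 5 lies near the mean and near 1.96 SDs. Under the second it lies near neither. These rules are guesses, because the plan states none. They show only that the labels decide whether 5 can be traced to this pilot.

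**Step 5: could the second pair be a different quantity?** The wording might mean lung score minus nose score. That is unlikely: the same two numbers would have to recur with their roles exchanged, MARS-5-L/N is the plan's name for the combined instrument, and the other pilot's lung and nose means differ by only 0.3 (20.7 − 20.4). If two quantities were meant, the text still needs to say so.

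**The case against.** The best defence is that the swap moves nothing. The stated 36 reproduces exactly without either pilot retest figure, and the calculation behind 47 rests on adherence percentages. The plan never says that its 5 points is the safe difference; that link is read from the order of the sentences. All of this stands, and it limits what can be claimed from the swap.

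Three stronger readings are tempting, and the documents do not support them.
- *That the swap invalidates the sample size.* It does not, because neither figure is an input to it.
- *That a target of 5 or 4 lies below the change seen without intervention, so a positive result could be ordinary retest change.* The protocol says only that patients were measured twice at least a month apart. It does not say what care they received in between, or whether the difference is signed or absolute.
- *That a mean retest shift would bias the comparison.* The trial is randomised and the target is a difference from controls. A shift common to both arms would largely cancel.

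It can also be said that 4 against 5 is a separate inconsistency. It is a distinct error, but both concern the same quantity: the target and where it came from. One might argue that 4 is a threshold of relevance and 5 a design difference. The plan draws no such distinction, and the two sentences are otherwise almost the same.

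**Conclusion.** Wrong as written: an internal inconsistency in the basis of the sample size. The reversal of mean and SD is on the page, and with no value or formula for the safe difference the basis of the target cannot be checked. That part is a fault of documentation and leaves 36 per group unchanged.

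The part with a numerical consequence is the target. For the primary outcome's 4 points, the plan's method needs 47 completers per group rather than 30, and the stated 80% becomes about 59% with 30 completers or about 72% with 39. The stated power therefore does not hold for the primary outcome as worded.

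These figures assume two-sided alpha 0.025, the normal approximation and the plan's SD of 6.28. Whether a single-scale SD suits the pooled 50-point score is a separate question, not settled here.

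**What to change.** 1. Check the pilot data and state once which of 5.34 and 2.62 is the mean and which the SD. Say what difference they describe: within-patient first to second measurement or lung against nose, and signed or absolute.
2. State one target value, the same in the research question, the primary outcome and the power calculation, and say how it was chosen. If it comes from the retest pilot, give the formula.
3. Restate the power for that target at the planned size, with completers and enrolled patients shown separately. Print alpha as 0.025 without the percent sign.

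The cost is a look-up in existing data and corrected wording. No added enrolment is required. If 5 stands, so does 36 per group. If 4 stands, the honest statement is a lower power at the planned size.

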to investigate patients' adherence with diseases of the global airways, and analyse whether patients' adherence with diseases of the global airways can be improved and whether this will contribute to increased disease control and significantly improved quality of life.

Purpose

To investigate the effect of systematic and structured nursing guidance in patients with global airways disease, CRSwNP and asthma primarily on adherence (measured on MARS-5- L/N), where the maximum score is 50 at 100% adherence for both diseases. As well as whether there is a change at the minimum in adherence in patients who receive systematic and structured guidance on disease and treatment compared to usual care which does not include structured guidance.

Hypothesis and research questions

Patients with respiratory diseases can improve their adherence to their non-medical and the medical treatment for CRSwNP/CRS and asthma by systematic and structured nursing guidance compared to patients who did not receive the above guidance.

In a randomized study, we will investigate whether the level of adherence measured by the questionnaire MARS-5-N and MARS-5-L in patients with CRSwNP/CRS and asthma can be improved by 5 points after systematic and structured nursing guidance at baseline visit and controlled after four months - compared with those patients who have not received the above guidance.

Outcomes

The primary outcome is to investigate whether the adherence rate measured by the MARS-5-N/L questionnaire in patients with CRSwNP and asthma can be improved by 4 points after systematic and structured nursing guidance at the initial visit and controlled after four months - compared with those patients who have not received the above guidance.

Secondary outcomes

- To demonstrate whether improved adherence can improve their sleep measured on a Epworth Sleepiness Scale - messured during a 4 month follow-up visits.

- To demonstrate whether improved adherence can improve their SNOT22 score by 9 points or more messured at a 4 month follow-up visits.

- To demonstrate whether improved adherence can improve their asthma control as measured by the ACQ messured at a 4 month follow-up visits.

- To demonstrate whether improved adherence can improve their asthma control as measured by ACT - measured at a 4 months follow-up visit.

- To demonstrate whether improved adherence can improve their quality of life as measured by the mini AQLQ messured at a 4 months follow-up visit.

06.05.2022

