and how their communication is with the practitioner (19,20). Adherence to inhaled medications is lower than to oral tablets or injectable medications. The more complex and the more times the patient has to remember to take the medication, the harder it is to establish optimal adherence (19,20).

CRSwNP a chronic disease like asthma, where low adherence is often seen in mild to moderate cases compared to severe cases of CRSwNP (21). However, the clinical perception is that not all patients take all their daily doses, but few scientific studies have focused on this. The difficulty in treating CRS is that the patient must apply nasal steroid 1-2 times daily as well as it must be combined with nasal saline irrigation at least once daily. Decreased adherence is led by poor disease control. It is therefore important to support and strengthen patient adherence to CRS and asthma in order to achieve good disease control (21).

Population and recruitment

The study population consists of patients referred to the Respiratory Clinic in the Department of Ear, Nose and Throat Surgery and Audiology, Rigshospitalet. Patients are recruited by initial visits to the Respiratory Clinic, where they receive oral and written information about the project. If patients wish to participate, they must complete a written consent form for participation in the project. In order to be included in the study, the following inclusion and exclusion criteria must be met:

Inclusion criteria	Exclusion criteria
Adherence to MARS- 5 L/N ≤35	Adherence to MARS-5- L/N >35
at first visit	points at first visit
Diagnosed with asthma (with and	Do not have smartphone
without allergic rhinitis) at initial	
visit	
Able to use smartphone	Does not read or speak English
Able to use smartphone	Does not read of speak Elignish
ACQ \geq 1.2 or ACT \leq 15 (partially	Other illness requiring regular
uncontrolled asthma)	medication
Be over 18 years of age	Pregnancy and pregnancy that
	started during the study time pe-
	riod
SNOT-22 score ≥35	Servere psychological comorbidi-
	ties
Diagnosed with CRSwNP	

Material and method

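### The 80% power behind 36 per group uses the SD of one 25-point scale, but the plan tests the pooled 50-point MARS-5-L/N score, for which no SD is given

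*Combined protocol and SAP*

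**What the plan says.** **The score.** The Purpose section describes MARS-5-L/N as a combined measure, "where the maximum score is 50 at 100% adherence for both diseases". Under Material and method, "Total MARS-5-N/L will be measured at their initial visit and four months after teaching or usual care". The entry limit under Population and recruitment, "Adherence to MARS- 5 L/N ≤35", exceeds the single-scale maximum of 25 and so must also refer to the total. The statistics section attaches its P<0.025 threshold to the pooled score.

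**The SD.** Material and method gives pilot results for each scale separately: "mean (SD) 20.4 (6.28) is found for MARS-5-L, and for MARS-5-N mean 20.7 (5.57) is found". The power calculation then reads "With a MIREDIF of 5 and the largest SD of 6.28 by single measurement", with alpha halved because there are two questionnaires and power set at 80%. It arrives at 36 per group including 20% dropout.

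**The target.** Under Hypothesis and research questions, adherence "can be improved by 5 points after systematic and structured nursing guidance at baseline visit". Under Outcomes, the primary outcome is whether it "can be improved by 4 points after systematic and structured nursing guidance at the initial visit".

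**Other figures.** A second pilot measured patients twice: "the mean of the inter-individual difference at MARS-5-L/N first and second time is equal to 5.34(2.62"). The statistics section repeats this as a mean with its SD, then gives the same two numbers as SD 5.34 and mean 2.62. A further calculation, 100% versus 80% adherence, gives 39 per group, or 47 with dropout. The analysis is described only as paired and unpaired tests, with rank-based alternatives.

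**The concern.** A power calculation must use the SD of the quantity that will be analysed. An SD of 6.28 with alpha 0.025 fits two single-scale tests. The plan instead describes one test of the sum of the two scales. Unless lung and nose scores are negatively correlated, the sum varies more than either part, so carrying 6.28 over to it would overstate power. The entry limit and a change-score analysis act in the other direction.

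Four gaps stop a reader from redoing the calculation:

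1. The target is 4 points in one place and 5 in another.
2. The between-arm comparison is not named (follow-up, change, or baseline-adjusted).
3. The roles of 5.34 and 2.62 are reversed between statements, or another quantity is meant.
4. Both 36 and 47 per group are given, and the text does not say which governs.

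As written, a reader of a null result could not tell whether the trial was large enough, and the open choices could be settled after the data are seen.

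**Working it through.** **Inputs from the documents.** SD 6.28 (lung) and 5.57 (nose); means 20.4 and 20.7, which sum to 41.1; difference 5 or 4; power 80%; entry at 35 or less. Alpha is printed as 0.025%, but the bracket 0.05/2 shows that 0.025 is meant. Sidedness is not stated; two-sided 0.025 reproduces the plan's figure.

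**1. The plan's figure.** (2.2414 + 0.8416)² = 9.505.
- 5 points: n = 2 × 9.505 × (6.28/5)² = 29.99, so 30 per arm; × 1.2 = 36, as stated.
- 100% versus 80%: n = 9.505 × 0.16/0.04 = 38.02, so 39; × 1.2 = 46.8, so 47, as stated.

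So 6.28 is the SD that produced 36. Below I use 30 and 39, the plan's own numbers before dropout. A literal 20% loss would leave slightly fewer (36 × 0.8 = 28.8; 47 × 0.8 = 37.6).

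**2. Single scale, SD 6.28 (noncentral t).**

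| Target | 30 per arm | 39 per arm |
|---|---|---|
| 5 points | 78% (80% by the plan's normal formula) | 89% |
| 4 points | 57% | 70% |

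For 4 points the plan's formula gives 2 × 9.505 × (6.28/4)² = 46.86, so 47 evaluable; × 1.2 = 56.4, so 57 enrolled. Even with 47 evaluable, the t-test gives 79%.

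**3. SD the trial can afford.** For 80% power on 5 points, the SD of the analysed quantity must be at most 6.1 at 30 per arm, or 7.0 at 39.

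**4. Pooled score.** With lung-nose correlation r, S = √(6.28² + 5.57² + 2r × 6.28 × 5.57). This is 8.39 at r = 0 and 10.27 at r = 0.5, and equals 6.28 only at r = −5.57/(2 × 6.28) = −0.44. These are SDs before the entry limit.

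To allow for entry at 35 or less, take a normal baseline with mean 41.1 and SD S, truncated at 35. The SD of the truncated baseline, √V, is 4.06 at r = 0 and 5.17 at r = 0.5. With retest correlation ρ:
- follow-up variance = ρ²V + S²(1 − ρ²)
- change variance = (1 − ρ)²V + S²(1 − ρ²)
- baseline-adjusted residual variance = S²(1 − ρ²)

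Assuming r from 0 to 0.5 and ρ from 0.6 to 0.8, for 5 points at two-sided 0.025:

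| Analysis | SD | Power at 30 | Power at 39 | Detectable at 80%, 30 / 39 per arm |
|---|---|---|---|---|
| Follow-up | 6.0-8.8 | 47-82% | 59-92% | 4.9-7.1 / 4.3-6.2 |
| Change | 5.1-8.5 | 50-93% | 63-98% | 4.2-6.9 / 3.6-6.0 |
| Baseline-adjusted | 5.0-8.2 | 53-94% | 66-98% | 4.1-6.7 / 3.6-5.8 |

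If the pooled score were tested once at 0.05, follow-up power would be 58-89% at 30 and 70-95% at 39.

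**5. If 5.34 were the SD of a signed pooled change.** The documents do not establish this. Power for 5 points would be 90% at 30 and 97% at 39; for 4 points, 72% and 84%. No figure is given for 2.62, because the pilot differences may be unsigned.

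**6. Ceiling.** The normal model ignores it, although the pilot mean plus one SD (20.4 + 6.28 = 26.7; 20.7 + 5.57 = 26.3) exceeds 25 on both scales. One assumed bounded shape (normals clipped to 5-25 and matched to the pilot means and SDs) gives power of 29-64% at 30 and 38-77% at 39 for follow-up, and 32-81% and 41-91% for change.

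**The case against.** The best reply is that the sponsor listed the available SDs and deliberately took the largest. If 5.34 is the SD of pooled change, 6.28 is conservative and power for 5 points is 90% or more. The hypothesis speaks of improvement, which suggests a change analysis, and the statistics section ends on 47 per group, so 36 may not be the operative size. This reading is plausible but not established: 5.34 is also given as a mean, no test is named, and neither size is declared to govern.

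A second reply is that halving alpha for two questionnaires implies two single-scale tests, for which 6.28 is on the right scale. The same section then applies 0.025 to the pooled score. Moreover, 6.28 is not adjusted for the entry limit, so even the single-scale 80% holds only if that SD applies to enrolled patients.

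Third, the pooled ranges rest on assumptions and span 80%. That is right. The bounded shape is the weakest of them: it puts about 49% of lung and 44% of nose pilot scores at exactly 25, and it assumes a t-test where the plan allows a rank test. The correlation range is not a firm bracket either. If 5.34 were the SD of lung minus nose, r would be about 0.60, outside the range, although the means differ by 0.3 (20.7 − 20.4), not 2.62.

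What stands of these replies is that a shortfall on the pooled score is not shown. They do not remove the mismatch, and they do not touch the 4-point result, which needs no assumed correlation.

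**Conclusion.** The concern holds. The figure of 36 is correctly computed, but with an SD that does not belong to the score the plan tests, and the documents do not allow the right one to be derived. Adequate and clearly inadequate power are both compatible with what is written. The pooled ranges illustrate this under assumed correlations and distributional shapes; they are not estimates of the trial's power.

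One shortfall rests on the plan's own inputs: the 4-point difference named as the primary outcome falls below 80% at both evaluable sizes. It would need 57 enrolled per arm by the plan's method, above both stated sizes. This should be corrected before the power statement is relied on.

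**What to change.** 1. Declare the primary endpoint. Either the pooled MARS-5-L/N score is the single primary endpoint, with one named between-arm analysis (follow-up, change, or baseline-adjusted) and one alpha (0.05 if it is tested once); or the two scales are tested separately at 0.025 each and the pooled score is not primary.
2. Reconcile 4 and 5 points.
3. State what 5.34 and 2.62 measure, whether the differences are signed, and which is the SD.
4. State whether 36 or 47 per group governs.
5. Restate the power, or the detectable difference, at that size, using the SD that matches the endpoint, the analysis and the entry limit. If the pilot recorded both scales in the same patients, take the SD from those data; otherwise give a range with the assumed correlations stated.

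The cost is protocol wording and one recalculation, and Material and method already says the pilots will feed a final power calculation. The fix itself requires no extra enrolment. The restated power may be less favourable. If it is below 80%, the sponsor must state and accept that, choose a more efficient analysis, or enlarge the trial.

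### The 47 per group is not sized for the 4-point primary outcome: the only score-based calculation uses 5 points and one subscale's SD, and 47 comes from an unlisted 100% versus 80% comparison

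*Combined protocol and SAP*

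**What the plan says.** All references are to the combined protocol and SAP.

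- **Effect.** Under Outcomes, the primary outcome is whether adherence on MARS-5-N/L "can be improved by 4 points after systematic and structured nursing guidance at the initial visit". Under Hypothesis and research questions, adherence "can be improved by 5 points after systematic and structured nursing guidance at baseline visit".
- **Score-based calculation.** Statistics data analysis and power calculation begins "With a MIREDIF of 5 and the largest SD of 6.28 by single measurement". It sets alpha at 0.05/2 and power at 80%, and arrives at 36 per group including 20% dropout.
- **Final number.** The next paragraph mentions both scales exceeding 80%, then continues: "hoping for 100% adherence in the intervention group, versus 80% in the control group, this would require 39 in each group". With 20% dropout this becomes 47 per group.
- **Source of the SD.** Under Material and method, "mean (SD) 20.4 (6.28) is found for MARS-5-L, and for MARS-5-N mean 20.7 (5.57) is found". So 6.28 belongs to MARS-5-L alone.
- **Score tested.** The statistics section says "A P-value <0.025 is considered significant for a pooled MARS-5-N and MARS-5-L" and gives the pooled score a maximum of 50. It also explains the split alpha by there being two schedules.
- **Difference data.** Material and method reports a repeat-measurement pilot in which the mean difference at the "first and second time is equal to 5.34(2.62)". The statistics section repeats this as a mean of 5.34, then gives a figure "which corresponds to an SD 5.34 and mean 2.62".

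**The concern.** The number that sets enrolment should follow from the primary outcome. Here the primary outcome is 4 points, the score-based calculation uses 5, and enrolment is set by a third quantity that is not among the listed outcomes as a between-arm comparison. The larger effect gives the smaller requirement, so the 4-point outcome is never openly sized.

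The SD is unsettled as well. A 25-point subscale, a 50-point total and a change score have different SDs, and the plan does not say which of these the test will use. A reader therefore cannot tell whether 47 per group is adequate, and a non-significant result could not be interpreted against a known power for the stated target.

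**Working it through.** **Inputs.** From the statistics section: alpha 0.025, power 80%, 5 points, SD 6.28, 20% dropout, and 36, 39 and 47 per group. From Outcomes: 4 points. From Material and method: subscale SDs 6.28 and 5.57, and the pair 5.34 and 2.62. Assumptions: tests are two-sided (the plan does not say), and the subscale correlation, which is not given, is ranged from 0 to 1.

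**1. Reproducing 36.** For two means, n = 2(z_α/2 + z_β)²(SD/Δ)².

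2 × (2.2414 + 0.8416)² × (6.28/5)² = 29.99, so 30 per group; 30 × 1.2 = 36.

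**2. Reproducing 39 and 47.** For two proportions with unpooled variance, n = (z_α/2 + z_β)² × [p₁(1−p₁) + p₂(1−p₂)]/(p₁−p₂)². With 1.00 and 0.80:

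(2.2414 + 0.8416)² × 0.16/0.04 = 38.02, so 39; 39 × 1.2 = 46.8, so 47.

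This uses the section's own alpha and power. The pooled-variance version gives 41.4, so 42. The result depends heavily on the 100%: with 95% versus 80%, the pooled-variance version gives 92 per group.

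**3. Requirement for 4 points at the plan's alpha and SD.**

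2 × (2.2414 + 0.8416)² × (6.28/4)² = 46.9, so 47 evaluable per group. That equals the number to be enrolled, before any dropout.

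**4. Power of 47 enrolled.** 47 × 0.8 = 37.6, taken as 37 evaluable per arm. Two-sided t-test (noncentral t), alpha 0.025:

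| SD | What the SD describes | 4 points | 5 points |
|---|---|---|---|
| 6.28 | one subscale, single measurement (plan's choice) | 67% | 87% |
| 5.34 | change score, if 5.34 is the SD of the change | 82% | 96% |
| 2.62 | change score, if 2.62 is the SD of the change | above 99% | above 99% |
| 8.4 | pooled score, assumed correlation 0 | 41% | 61% |
| 11.9 | pooled score, assumed correlation 1 | 21% | 32% |

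Pooled SD = √(6.28² + 5.57² + 2r × 6.28 × 5.57), which is 8.39 at r = 0 and 11.85 at r = 1.

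With no dropout (47 evaluable) and SD 6.28, power for 4 points is 79% by the t-test. The largest SD at which 37 per arm still gives 80% power is 5.48 for 4 points and 6.85 for 5.

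**5. Dropout.** Multiplying by 1.2 does not allow for 20% loss: 36 × 0.8 = 28.8 (30 needed) and 47 × 0.8 = 37.6 (39 needed). The loss actually covered is 1 − 30/36 = 16.7% and 1 − 39/47 = 17.0%. Dividing by 0.8 gives 30/0.8 = 37.5, so 38, and 39/0.8 = 48.75, so 49.

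**The case against.** The best defence is that 39 has a recoverable basis. The same sentence names a criterion (both scales above 80%), the section assigns chi-square to categorical variables, and two proportions at the section's own alpha and power give 39. This stands. A reader might infer that 39 is an arithmetic error, or that it has no endpoint or test behind it at all; the documents support neither. The same 39 also follows from 4 points at SD 6.28 and alpha 0.05 (38.7), so one might suppose that the primary outcome was sized after all. The plan does not say so, and its alpha is 0.025. What the defence does not supply is a listed between-arm outcome of this kind, a test, alpha and power tied to this calculation, or a source for the 100%.

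A second objection is that the low pooled-score figures depend on one reading. This also stands in part. The reference to two schedules and the choice of the larger SD fit two separate subscale tests, for which 6.28 is the cautious choice. The same section nevertheless attaches 0.025 to a pooled score, so the text leaves the matter open.

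Third, much of the shortfall for 4 points comes from the assumed 20% loss: power is 79% without dropout against 67% with it. That is correct, but 20% is the plan's own figure.

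Finally, a reader might conclude that the trial is simply underpowered. The documents do not support this. At 5 points and SD 6.28 the 80% target is met. If change scores are compared and either printed difference figure is their SD, it is met for 4 points too.

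**Conclusion.** The statistics section does not size the trial for its stated primary outcome, and the plan gives no power for 4 points at 47 per group. With 37 evaluable per arm, a two-sided test at 0.025 and the plan's SD of 6.28, power is 87% for 5 points and 67% for 4. The unresolved choice between 4 and 5 points therefore decides whether the 80% target is met. Which score is analysed matters even more: for 4 points, power runs from 21% (pooled score, assumed correlation 1) to above 99% (change score with SD 2.62).

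These figures rest on two-sided testing, 20% dropout rounded down to 37 per arm and, for the pooled score only, the assumed correlation. The 39 is not shown to be wrong; it answers a question that the outcome list does not ask. The dropout shortfall is real but small, at two patients per arm.

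**What to change.** 1. Reconcile 4 and 5 points across Hypothesis, Outcomes and the statistics section, and name one primary effect.
2. Name the score analysed (subscale or pooled; four-month value or change) and use the SD of that score. Reconcile which of 5.34 and 2.62 is the mean and which the SD, and which difference they describe.
3. Keep 47 per group and replace the 100% versus 80% justification with the power that 47 delivers. Suggested wording: *With 47 per group and 20% dropout (37 evaluable), a two-sided test at 0.025 has X% power for [effect] at SD [value] of [score].* Add sensitivity labelled by quantity. For 4 points: 67% at 6.28 (one subscale, single measurement); 82% at 5.34 or above 99% at 2.62 (only if change scores are compared and that figure is the SD of the change); 41% to 21% at 8.4 to 11.9 (pooled score, assumed correlation 0 to 1).
4. State that 36 and 47 allow for about 17% dropout, or correct them to 38 and 49.

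**Cost.** A rewritten paragraph and, unless the relevant SD is about 5.5 or less, a less favourable stated power for 4 points. Keeping 47 adds no patients; moving to 49 adds 2 × (49 − 47) = 4 in total.
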